### **Psoriasis Area and Severity Index (PASI) Evaluation**

A qualified physician or qualified designee will perform the PASI assessment at the designated study visits identified in [Table 1](#). The site will make every attempt to have the same investigator or qualified designee perform this assessment throughout the study for

each subject. All raw data used to determine the PASI will be documented on a worksheet and transcribed onto the appropriate eCRF. The PASI worksheets will be kept by the site in the subject's source documentation. Information and instructions on the calculation of the PASI score are provided in [Appendix D](#). AbbVie will provide training for any Investigator or qualified designee who has not previously performed the PASI assessment.

#### **Physician's Global Assessment (PGA) of Ps**

The PGA is a 6-point scale used to measure the severity of a subject's Ps. The Investigator or qualified designee will perform a PGA of Ps ([Appendix E](#)) at the designated study visits identified in [Table 1](#). The site will make every attempt to have the same investigator or qualified designee perform this assessment throughout the study for each subject.

**Dermatology Life Quality Index (DLQI)**

Subjects will complete the DLQI at Baseline and Weeks 8, 16 and 24. Details of the DLQI are provided in [Appendix F](#).

**Body Surface Area Affected by Ps**

Body surface area affected by Ps will be measured at the designated study visits indicated in [Table 1](#). The subject's hand should be used as the measuring device. For purposes of clinical estimation, the total surface of the palm plus five digits will be assumed to be approximately equivalent to 1%. Measurement of the total area of involvement by the Investigator or qualified designee is aided by imagining if scattered plaques were moved so that they were next to each other and then estimating the total area involved. The site will make every attempt to have the same investigator or qualified designee perform this assessment throughout the study for each subject.

**Clinical Laboratory Tests**

For this study, Investigators will use a central laboratory for all laboratory tests and should follow the instructions regarding processing and shipment of samples provided by the laboratory and AbbVie.

Blood and urine samples will be obtained for clinical laboratory tests. When blood draws are performed as part of a clinic visit, the draws should be performed after completion of questionnaires and vital sign measurement, and before study drug administration. Blood specimens for hematology and chemistry will be obtained at Screening, Baseline and Weeks 8, 16 and 24 study visits. Blood specimens will also be drawn at the same visits for analysis of ADA serum concentrations; in this case it is particularly important that blood samples be drawn before administration of ADA.

Urine samples will be obtained for urinalysis testing at Screening, Baseline, and Weeks 8, 16, and 24. The central laboratory should perform a macroscopic urinalysis (urine dipstick) on the collected urine specimens. Specified abnormal macroscopic urinalyses

defined as leukocytes, nitrite, protein, ketones or blood greater than negative, or glucose greater than normal should be followed up with a microscopic analysis at the central laboratory.

All required clinical laboratory tests are outlined in [Table 2](#).

**Table 2. Clinical Laboratory Tests**

Chemistry	Hematology	Urinalysis	Quantiferon TB Gold	Other
Albumin	Basophils	Blood	Quantiferon Mit.	ANA Pattern
Alkaline Phosphatase	Eosinophils	Glucose, Urine	minus NIL	Anti-ds DNA
ALT	HCT	Ketones	Quantiferon NIL	Antinuclear
AST	HGB	Leukocytes	Quantiferon TB	Antibody
Calcium	Lymphocytes	Nitrite	Gold	C-Reactive Protein,
Cholesterol	Monocytes	pH	Quantiferon TB	HS
Creatinine, Enzymatic	Neutrophils	Protein, Urine	minus NIL	HBV DNA PCR
Glucose, Random, Serum	Platelets	Specific Gravity		Taqman
Phosphate	RBC	Urine Microscopic		HCG, Quantitative
Potassium	WBC			Hep B Core Ab
Sodium				Hep B Surface Ab
Total Bilirubin				Hep B Surface Ag
Total Protein				HIV 1 & 2 EIA Ab Screen
Triglycerides				Hep C Ab Screen
Urea (BUN)				
Uric Acid				

### Hepatitis B and Hepatitis C Testing

All subjects will be tested for the presence of the Hepatitis C Virus (HCV) and Hepatitis B Virus (HBV) at Screening. A positive result for Hepatitis C and/or Hepatitis B surface antigen (HBs Ag) will be exclusionary. Samples that are negative for HBs Ag will be tested for surface antibodies (HBs Ab) and core antibodies (HBc Ab Total). Subjects with HBs Ag (-), HBs Ab (-), and HBc Ab Total (+) require PCR qualitative testing for HBV DNA. Any HBV DNA PCR result that meets or exceeds detection sensitivity will be

---

exclusionary. Also, subjects showing a positive HBc Ab Total test, indicating a previous Hep B exposure, will be excluded due to risk of reactivation or worsening of hepatitis B with MTX.

Subjects with a negative HBs Ag test and tests showing the results below, do not require HBV DNA PCR qualitative testing.

- HBc Ab Total (-) and HBs Ab (-)
- HBc Ab Total (-) and HBs Ab (+)
- HBc Ab Total (+) and HBs Ab (+)

### **Human Immunodeficiency Virus (HIV) Testing**

Documentation from the physician that subjects are not known to be HIV positive or do not have a high risk for HIV infection will be sufficient for this study. Details of this documentation should be recorded in the eCRF. However, in the absence of such documentation subjects should be tested for antibodies to HIV at Screening, and test results documented. A subject will not be eligible for study participation if test results indicate a positive HIV infection. AbbVie will not receive results from any testing and will not be made aware of any positive result.

### **Immunologic Laboratory Testing**

High sensitivity C-reactive protein (hs-CRP), antinuclear antibody (ANA) and anti-double-stranded DNA (anti-dsDNA) assessments will be performed in a central laboratory as indicated in [Table 1](#).

### **Pregnancy Tests**

A serum pregnancy test will be performed at the Screening visit on all female subjects of childbearing potential. At the Baseline visit, as well as at week 8, 16 and 24, subjects of childbearing potential will have a urine pregnancy test performed locally by designated study personnel. If any urine pregnancy test is positive, a serum pregnancy test will be

performed. A lactating or pregnant female will not be eligible for participation or continuation in this study.

Females of non-childbearing potential (either postmenopausal or permanently surgically sterile as defined above) at Screening do not require pregnancy testing.

### **Pharmacokinetic (PK)/serum ADA Sampling**

Blood collection will be performed prior to medication dosing according to the visit schedule outlined in [Table 1](#). Refer to Section [5.3.2](#) for sample collection and handling instructions.

### **Subject Enrollment**

All Screening laboratory results must be reviewed, signed and dated by the Principal Investigator or Sub-Investigator at each site prior to the Baseline visit. Subjects will not be enrolled into the study if laboratory or other Screening result abnormalities are deemed clinically significant by the Principal Investigator or sub-Investigator.

Subjects should continue to receive adalimumab every other week during the screening period (if applicable) and the Baseline visit should coincide with the next planned dose of ADA.

### **Adverse Events**

AEs will be assessed at every study visit from the first dose of study medication through to Week 24 study visit, and during the 70-day safety phone call after the last dose of ADA (or until the subject begins use of commercially available ADA, whichever comes first). In addition, all serious adverse events (SAEs) will be captured from the time the subject signs the Informed Consent Form through study completion or Premature Discontinuation and at the 70-day safety follow-up. Any new AEs/SAEs reported during the 70-day follow-up period should be submitted to AbbVie. The 70-day safety follow-up phone call

will be recorded in source documents only and confirmation of the contact will be faxed to AbbVie (Refer to Section [5.4.1](#) and [Appendix G](#) for additional information).

### **ADA Wash-Out**

This is restricted to potentially eligible subjects who on identification by the Investigator, are receiving ADA at a dose of 40 mg once weekly. These subjects should be initiated on ADA 40 mg eow for at least 8 weeks prior to screening. Documentation on date of initiation of wash-out and confirmation of all additional inclusion criteria must be recorded in the eCRF.

### **Study Medication Dispensing**

ADA and MTX will be dispensed to subjects beginning at Baseline, at Weeks 8 and 16; no study medications will be dispensed at Week 24. Refer to Section [5.5](#) for additional information.

### **Subject Dosing Diary**

All subjects will be given a subject dosing diary to record all ADA injection dates and times and MTX weekly dosing schedules. Subjects should also record missed ADA and MTX doses in their dosing diary.

### **Unscheduled Visit**

If required, an unscheduled visit can be performed according to the visit schedule outlined in [Table 1](#). If the unscheduled visit falls within 7 days of the next planned visit, and if all the required procedures of the planned visit are performed, the unscheduled visit accounts for the planned visit. The CRF for the planned visit should be completed.

---

**5.3.2                   Drug Concentration Measurements****5.3.2.1               Collection of Samples for Analysis**

Blood samples for the measurement of serum ADA concentrations will be collected at Baseline, Weeks 8, 16 and 24. Blood samples should be drawn prior to administration of both ADA and MTX.

**5.3.2.2               Handling/Processing of Samples**

The blood samples for PK measurements will be centrifuged within 60 minutes of collection to separate the serum. The serum samples will be transferred using sterile plastic pipettes into screw-capped polypropylene vials labeled with the study drug number, protocol number, subject number, and study week. The serum samples will be frozen within 2 hours after collection and will remain frozen in a -20°C or colder freezer after collection until shipment. Sites that do not have access to a -20°C or colder freezer must ship the samples the day they are collected.

Sample collection and handling instructions will be provided by the central laboratory to the investigative sites.

**5.3.2.3               Disposition of Samples**

The frozen serum samples will be packed in dry ice (pellet form) sufficient to last 3 days during transport. Samples will be shipped pursuant to instructions from the central laboratory. An inventory of the samples will be included in the package for shipment. The investigative site will need to identify a dry ice source and will be responsible for purchasing the necessary amount of dry ice for shipment of frozen samples. Shipping kits for the samples will be provided by the central laboratory.

Arrangements will be made with the central laboratory for the transfer of samples.

---

**5.3.2.4                    Measurement Methods**

Serum concentrations of ADA will be determined using a validated assay method. All methods will be performed under the supervision of the Drug Analysis Department at AbbVie.

**5.3.3                    Efficacy Variables****5.3.3.1                    Primary Variable(s)**

The primary efficacy endpoints will be:

- Based on Investigator assessment, the proportion of subjects (primary and secondary sub-optimal responders at baseline) achieving a satisfactory response to ADA + MTX treatment after 16 weeks (satisfactory response defined as highly or completely satisfied with subject's therapy based on responses to the satisfaction questionnaire);
- Based on subject self-assessment, the proportion of subjects (primary and secondary sub-optimal responders at baseline) achieving a satisfactory response to ADA + MTX treatment after 16 weeks (satisfactory response defined as highly or completely satisfied with therapy based on responses to the satisfaction questionnaire).

**5.3.3.2                    Secondary Variable(s)**

Secondary efficacy endpoints will include:

- The proportion of subjects (primary and secondary sub-optimal responders at baseline) achieving 50%, 75%, 90% and 100% reductions in PASI at 8, 16 and 24 weeks after initiation of ADA + MTX (change in PASI based on score at initiation of ADA + MTX therapy);
- The proportion of primary sub-optimal responders achieving 50%, 75%, 90% and 100% reductions in PASI at 8, 16 and 24 weeks after initiation of ADA + MTX (change in PASI based on score at initiation of ADA + MTX therapy);

- 
- The proportion of secondary sub-optimal responders achieving 50%, 75%, 90% and 100% reductions in PASI at 8, 16 and 24 weeks after initiation of ADA + MTX (change in PASI based on score at initiation of ADA + MTX therapy);
  - The proportion of subjects on ADA 40 mg eow prior to baseline or 40 mg once weekly prior to wash-out achieving 50%, 75%, 90% and 100% reductions in PASI 16 weeks after initiation of ADA + MTX (change in PASI based on score at initiation of ADA + MTX therapy);
  - Proportion of primary and secondary sub-optimal responders achieving a clinical response defined as a PGA of “Clear” or “Minimal” at 8, 16 and 24 weeks after initiation of ADA + MTX;
  - DLQI scores at baseline (at initiation of ADA + MTX) and at weeks 8, 16 and 24;
  - Change and percent change in DLQI from baseline to weeks 8, 16 and 24;
  - Proportion of subjects with each of the five categories of satisfaction with treatment at baseline (at initiation of ADA + MTX) and at weeks 8, 16 and 24 (subject self-assessment and Investigator assessment using the satisfaction questionnaires);
  - Proportion of primary and secondary sub-optimal responders achieving a DLQI score of 0 or 1 at 8, 16 and 24 weeks after initiation of ADA + MTX;
  - Serum levels of ADA in subjects at baseline (at initiation of ADA + MTX) and at weeks 8, 16 and 24.

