sub-optimal response to current ADA monotherapy, subjects eligible for participation in the study must have a PGA score of  $\geq 3$  and a PASI of  $\geq 5$ . Data collected at a screening visit will include: subject demographics, disease history, comorbidities, vital signs, laboratory investigations and PGA, PASI and DLQI scores. Starting at the baseline visit (Day 0), subjects will continue to self-administer ADA (40 mg eow) and will have oral MTX added to their treatment at a dose to be defined by the Investigator (between 10 mg and 25 mg per week). All subjects will also receive the non-investigational medicinal product oral folic acid as a dietary supplement since MTX acts as a folic acid antagonist. The folic acid tablets will be provided by the Investigator at a dose of 1.0 mg per day. The required folic acid dose must be taken every day of the week except on the day when MTX is taken. The Investigator will provide specific instructions on the number of folic acid tablets each subject should take.

In the event a subject forgets to take the tablets or takes more or less than is required, they will be instructed to contact the Investigator for guidance. Unused folic acid tablets should be returned to the investigative site and accounted for to assess subject's compliance.

At site visits 8, 16 and 24 weeks after initiation of ADA/MTX, the following parameters will be assessed: Investigator assessment of disease status (using a satisfaction questionnaire); subject self-assessment of disease status (using a satisfaction questionnaire); PGA; PASI; DLQI; AEs; serum levels of ADA. A schematic of the study design is shown in [Figure 1](#).

The 70-day safety follow-up period begins from the last dose of ADA. Subjects will be discontinued from the study if they withdraw consent or if they are deemed unsuitable to continue for any reason by the Investigator in consultation with the AbbVie Medical Monitor.

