### **Satisfaction with Treatment Evaluation**

Satisfaction with treatment will be assessed using a questionnaire similar to one developed by Christophers et al (28) for quantifying physician and Ps subject satisfaction with biologic therapy. In this study, dermatologists and subjects were surveyed regarding their satisfaction with therapy using the following questions:

Dermatologist survey question: Overall, at this point in time, how satisfied are you with the Ps control provided by the subject's current treatment regimen?

Subject survey question: Overall, how satisfied are you with your current treatment for Ps?

The same questions will be used in the present study. The response choices provided will be:

- Completely dissatisfied
- Moderately dissatisfied
- Slightly satisfied
- Highly satisfied
- Completely satisfied

Within the context of the study, Investigators indicating complete or moderate dissatisfaction with treatment will be combined to indicate subjects eligible for the study during screening (i.e., subjects with a sub-optimal response to ADA). Satisfaction with therapy will be defined by the combination of highly or completely satisfied responses. The questionnaires will be administered during screening and after 8, 16 and 24 weeks of ADA/MTX. Additional details of the questionnaire structure are provided in [Appendix C](#).

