## **5.6 Discussion and Justification of Study Design**

### **5.6.1 Discussion of Study Design and Choice of Control Groups**

This is a single arm, open label, longitudinal study designed to assess the impact of addition of oral MTX to ADA therapy in subjects with Ps who are not responding optimally to ADA monotherapy, either as primary or secondary sub-optimal responders. Sub-optimal response in this case means subjects with an unsatisfactory response to treatment based on an Investigator assessment. Subjects must also have a PGA  $\geq 3$  and a PASI of  $\geq 5$  to be eligible for participation in the study. Efficacy is based on the proportion of subjects with a satisfactory response to ADA + MTX therapy, based on subject self-assessment and an assessment by the Investigator; Ps related clinical

---

outcomes will also be assessed as will the relationship between serum ADA levels and degree of clinical response. There is no control group in this study; instead each subject serves as their own control and outcomes after addition of MTX are compared to similar assessments at Baseline, prior to the addition of MTX to ADA therapy.

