5.0 Analysis Populations

5.1 Definition of Analysis Populations

Intent-to-Treat (ITT) Populations

The Intent-to-Treat population will be used for all efficacy analyses, which is defined as all subjects who receive at least one dose of study ADA and at least one dose of MTX during the study.

The primary efficacy analyses will also be conducted for the following sub-populations:

- ITT Subjects who are defined as primary sub-optimal responders at baseline based on Investigator assessment.
- ITT Subjects who are defined as secondary sub-optimal responders at baseline based on Investigator assessment.

Safety Populations

The Safety Population will be used for all safety analysis, which is defined as all subjects who received at least one dose of study ADA and one dose of MTX during the study. In this study, the safety population is the same as the ITT Population.

Notations for Treatment Groups

- ADA/MTX: Subjects who received ADA and MTX as study drugs.

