10.0 Efficacy Analysis

10.1 General Considerations

Point estimates and 95% confidence intervals (CIs) based on normal approximation will be provided for the discrete efficacy variables such as the proportion of responders to ADA/MTX. Change and percent change from baseline variables will be estimated using an appropriate estimation from a Mixed Model and statistical tests of change from baseline equal to zero will be carried out at the 0.05 significance level; 95% confidence intervals will also be provided.

Descriptive statistics will be provided. These include the number of observations, mean, and standard deviation for continuous variables and counts and percentages for discrete variables. Baseline and visit means at each scheduled visit will also be provided for change and percent change from baseline continuous variables.

Missing data will be imputed using the following methods for the efficacy analyses:

- Non-Responder Imputation (NRI): The NRI analysis will categorize any subject who has missing value at a specific visit as non-responder (or "dissatisfied" in satisfaction variables) for that visit. NRI will be the primary approach in analyses of categorical variables.
- Mixed-effect Model Repeat Measurement (MMRM): A mixed-effect model will be developed for continuous endpoint repeated measured at Baseline, Week 8, 16, and 24; controlling for time and subject ID. The fixed effects will be used to report the visit means at corresponding visits. Change and percent

change from baseline will be determined accordingly. MMRM will be the primary approach in analyses of continuous variables.

- Last Observation Carried Forward (LOCF): The LOCF analyses will use the completed evaluation from the previous visit to impute missing data at later visits. Baseline efficacy evaluations will not be carried forward. LOCF will be a sensitivity approach in analyses of continuous variables and categorical variables.

All efficacy variables will be analyzed for the ITT population overall, and separately by primary sub-optimal responders and secondary sub-optimal responders at baseline.

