10.2.2 Secondary Efficacy Variables

Secondary efficacy variables included:

- Based on investigator assessment, the proportion of subjects achieving a satisfactory response at scheduled visits other than Week 16
- Based on subject self-assessment, the proportion of subjects achieving a satisfactory response at scheduled visits other than Week 16
- Proportion of subjects achieving PASI 50/75/90/100 at all scheduled visits

- Change and percent change from baseline in PASI at all scheduled visits.
- Proportion of subjects achieving a clinical response defined as a PGA of "Clear" or "Minimal" at all scheduled visits
- Change and percent change from baseline in DLQI at all scheduled visits
- Based on investigator assessment, the proportion of subjects at each of the five categories of satisfaction at all scheduled visits
- Based on subject self-assessment, the proportion of subjects at each of the five categories of satisfaction at all scheduled visits
- Proportion of subjects achieving a DLQI score of 0 or 1 at all scheduled visits
- Change and percent change from baseline in BSA at all scheduled visits.
- Change from baseline in hs-CRP at all scheduled visits.

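### The DLQI 0/1 rate counts subjects already at 0 or 1 before MTX is added, because entry sets no DLQI minimum; an analysis of subjects with baseline DLQI of 2 or more should sit beside the ITT figure

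*Protocol*

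**What the plan says.** **Endpoint.** Protocol 5.3.3.2 defines it as the "Proportion of primary and secondary sub-optimal responders achieving a DLQI score of 0 or 1 at 8, 16 and 24 weeks" after combination therapy starts. SAP 10.2.2 has "Proportion of subjects achieving a DLQI score of 0 or 1 at all scheduled visits". Neither places a condition on the baseline score.

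**Denominator.** SAP 10.1 states: "All efficacy variables will be analyzed for the ITT population overall, and separately by primary sub-optimal responders and secondary sub-optimal responders at baseline". SAP 5.1 defines ITT as "all subjects who receive at least one dose of study ADA and at least one dose of MTX during the study". Protocol 8.1.4 also fixes ITT as the set for secondary as well as primary efficacy. Missing visits in categorical endpoints count as non-response (NRI, SAP 10.1).

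**Entry.** Under Protocol 5.1, "subjects eligible for participation in the study must have a PGA score of" at least 3 and a PASI of at least 5. The third requirement is the Investigator's own dissatisfaction: "Investigators indicating complete or moderate dissatisfaction with treatment will be combined to indicate subjects eligible for the study during screening" (Protocol 5.3.1.1). Nothing in Protocol 5.2.1 or 5.2.2 refers to DLQI or to the subject's own satisfaction.

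**Baseline data.** Protocol 5.3.1.1: "Subjects will complete the DLQI at Baseline and Weeks 8, 16 and 24". SAP 7.1 summarises baseline DLQI.

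**Comparator.** Protocol 5.6.1 has no control group; each subject's later results are set against his or her own baseline.

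**The concern.** The other responder endpoints on the secondary list cannot already be met when MTX starts. PASI 50, 75, 90 and 100 are reductions from the score at that point. PGA Clear or Minimal (0 or 1) is excluded by the PGA entry rule, which Protocol 5.3.1.1 applies at both Screening and Baseline. DLQI 0/1 has no such protection: it is a patient-reported level, while eligibility rests wholly on physician ratings.

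Protocol 4.2 uses DLQI to judge how large the benefit of adding MTX is, when it appears and whether it lasts. A subject at 0/1 throughout counts as a response by Week 8 that is sustained to Week 24, although nothing changed. With no control arm, no other part of the design subtracts that share. The share could also differ between primary and secondary sub-optimal responders, so their DLQI 0/1 rates could differ for that reason alone.

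**Working it through.** **1. The plan's own figure.** The documents give no planning figure for DLQI 0/1. Their precision tables (Protocol Table 5, SAP Table 2) are for the satisfaction endpoints, but the formula carries over: half-width = 1.96 × √(p(1−p)/n). At p = 0.20, n = 50: 1.96 × √(0.16/50) = 11.1 points, as tabulated. All ten rows for n = 50 reproduce to rounding.

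**2. Can a subject enter at DLQI 0/1?** The criteria allow it. Under the PASI formula in Protocol Appendix D, disease confined to the lower extremities with erythema 3, induration 2, desquamation 2 and area score 2 gives 0.4 × (3+2+2) × 2 = 5.6, above the threshold of 5. This shows only that limited disease can meet the PASI rule. It does not show how often such a subject would also have PGA of at least 3 and report almost no life impact.

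**3. Formula.** Let
- q = share of ITT at DLQI 0/1 at baseline,
- s = share of those counted at 0/1 at the visit,
- r = share of the remaining subjects counted at 0/1 at the visit.

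ITT rate = q·s + (1−q)·r. Excess over r = q·(s − r). It is positive only if s > r, and zero if q = 0.

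**4. Numbers.** All values of q, s and r are assumptions; the documents give none.

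| q | s | r | ITT rate | Excess (points) |
|---|---|---|---|---|
| 0% | any | 20% | 20.0% | 0 |
| 4% (2 of 50) | 70% | 25% | 2.8 + 24.0 = 26.8% | 1.8 |
| 10% (5 of 50) | 70% | 25% | 7.0 + 22.5 = 29.5% | 4.5 |
| 10% | 90% | 15% | 9.0 + 13.5 = 22.5% | 7.5 |
| 20% (10 of 50) | 90% | 15% | 18.0 + 12.0 = 30.0% | 15.0 |
| 10% | 100% | 0% | 10.0 + 0 = 10.0% | 10.0 |

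In the last row nobody benefits, and the endpoint reports the baseline share as achievement. At q = 10%, an excess of 4.5 to 7.5 points is 0.4 to 0.7 of the 11.1-point half-width (4.5/11.1 and 7.5/11.1).

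**5. Precision lost by restricting to baseline DLQI of at least 2.** At a 20% rate:
- n = 48: 1.96 × √(0.16/48) = 11.3 points
- n = 45: 1.96 × √(0.16/45) = 11.7 points
- n = 40: 1.96 × √(0.16/40) = 12.4 points

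**The case against.** **The size is assumed, and such subjects may be few.** This stands. Entry needs PGA of at least 3, PASI of at least 5 and a dissatisfied Investigator, and Protocol 3.2 itself describes a substantial effect of psoriasis on quality of life. Nothing in the documents supports the 20% case in particular.

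**The direction is not guaranteed.** This also stands. One DLQI item asks about the burden of treatment, and MTX adds treatment. NRI turns any baseline-0/1 subject with a missing visit into a non-responder. Both lower s. A reader might infer that the rate is always inflated; the documents support only a conditional statement (q > 0 and s > r), with s > r the expected case.

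**DLQI is already reported in other ways.** Baseline scores are summarised, and change and percent change are separate endpoints estimated by a mixed model. These help, but none links a baseline score of 0/1 to later response. SAP 10.2.2 refers to all scheduled visits, and SAP Table 4 lists Baseline as a scheduled week, so a baseline proportion may be intended. Neither document commits to one, and it would not be enough. With q = 10%, s = 80% and r = 20%, the ITT rate is 8.0 + 18.0 = 26.0%, and subtracting the baseline 10% gives 16.0%, not 20%, because gains and losses are netted.

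**The ITT proportion correctly estimates what it defines.** True: as the share of ITT subjects at 0/1 at a visit, it is unbiased. The difficulty arises when it is read as the benefit of adding MTX, which the wording and the design invite. A reader might infer that ITT should be demoted to a supplementary line. Protocol 8.1.4 does not support that, because it requires ITT for secondary efficacy.

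**Conclusion.** The structural point holds in both documents: an absolute threshold, all ITT subjects in the denominator, no DLQI entry minimum, and no control arm. Subjects at 0/1 on ADA alone who stay there are counted as achieving the endpoint. If such subjects enrol and s exceeds r, the ITT rate overstates the benefit of adding MTX by q·(s − r): 4.5 to 7.5 points at an assumed q of 10%, and 1.8 to 15.0 points over the wider assumed range of 4% to 20%. It is zero if nobody starts at 0/1. The documents cannot settle which case applies.

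A reader might also infer that the trial's main conclusion is at risk. It is not. This is one of several secondary variables, no test is specified for the proportion, and the primary satisfaction endpoints do not use DLQI. The effect is confined to interpretation of this one rate.

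**What to change.** In SAP 10.2.2, keep the DLQI 0/1 proportion in all ITT subjects, as Protocol 8.1.4 requires, and add:

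- (a) the DLQI 0/1 rate at Weeks 8, 16 and 24 among ITT subjects with baseline DLQI of at least 2, overall and by primary and secondary sub-optimal responder, with NRI, named as the figure used to interpret the benefit of adding MTX;
- (b) the number of ITT subjects at 0/1 at baseline, and a shift table from baseline to each visit (0/1 versus 2 or more).

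Use the SAP 6.1 baseline, and state where subjects with no baseline DLQI are counted.

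The cost is a few lines of SAP text and one extra table, with no new data collection. Analysis (a) has a slightly smaller denominator: at a 20% rate the half-width goes from 11.1 points (n = 50) to 11.7 (n = 45). If nobody starts at 0/1 and no baseline DLQI is missing, (a) equals the ITT result.
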